6.15.2.8. Knee Flexion

The subject is seated in a hardback chair with the hip flexed to 90 degrees and a towel roll placed under the knee of the leg being. They should rest their hands in their lap or at their side, and not hold onto the chair. The knee is partially extended to 45 degrees. The leg being tested is raised off the floor, with the opposite foot on the floor. The hand held dynamometer is placed 2(two) inches proximal to the posterior ankle. The evaluator stabilizes at the anterior proximal knee joint to prevent hip flexion. The subject bends their knee against the resistance of the dynamometer. Evaluator should match the subject's resistance for at least two seconds before increasing their force to break the contraction. The number is recorded, the dynamometer is reset to zero, and the test repeated.

6.15.2.9. Ankle Dorsiflexion

The subject is seated in a hard back chair with the knee extended and the heel resting on a towel roll placed on the floor. They should rest their hands in their lap or at their side, and not hold onto the chair. The ankle is in 0 degrees (neutral) dorsiflexion (foot perpendicular to the lower leg). The opposite foot remains flat on the floor. The hand held dynamometer is placed proximal to the metatarsal joints on the dorsum of the foot just lateral to the great toe. The evaluator stabilizes at the anterior proximal knee joint. Evaluator should match the subject's resistance for at least two seconds before increasing their force to break the contraction. The number is recorded, the dynamometer is reset to zero and the test repeated.

6.15.3. Appendix 3: Procedure for IT transplantation of MSC-NTF cells

The purpose of this document is to describe the procedure and define the basic requirements for Intrathecal (IT) Transplantation of BrainStorm's proprietary MSC-NTF cells in clinical trials.

The procedure described here is based on common clinical practice (standard lumbar puncture procedure) as well as the experience of the medical staff currently conducting the company's clinical trial at the Neurology Department of the Hadassah Medical Center in Jerusalem.

6.15.3.1. Product Handling and injection procedures

All syringes should be gently rotated for 20-30 seconds until all cells are in suspension.

For IM injections remove syringe cap and connect a 25Gx5/8" (0.5 x 16 mm) needle.

With the needle in the upright position gently flick the syringe to surface any trapped bubbles. Push the plunger up until the first drop is visible at the tip of the needle. At this point the product is ready for injection.

For IT injections gently remove syringe cap. With the syringe in the upright position gently flick syringe to surface any trapped bubbles. Slowly and carefully push plunger up, until the liquid meniscus is visible at the top of the (needle-less) syringe. Connect syringe to the 3rd outlet of the valve, and inject the cells over roughly 2 minutes (see section 6.15.3.2. below).

6.15.3.2. IT Injection Procedure:

1. When performing IT transplantation of MSC-NTF cells, the patient is typically placed in a left (or right) lateral position with his/her neck bent in full flexion and knees bent in full flexion up to his/her chest, approximating a fetal position as much as possible.
2. The area around the lower back is prepped using aseptic technique. A 20 G, 3.5 inch, 0.9x90 mm spinal needle (such as: BD Cat. No. 405253) is inserted between the lumbar vertebrae L3/L4 or L4/L5 to a depth at which there is a "give" indicating that the needle is past the ligamentum flavum.
3. The needle is inserted further until there is a second 'give', indicating that the needle is now past the dura mater and in the subarachnoid space.
4. The stylet from the spinal needle is then withdrawn and a 3-way stopcock (such as Elcam Medical Cat. No. 582682) is immediately attached to the spinal needle.
5. A 3 to 5 ml syringe, with the plunger drawn back, is attached to the 2nd outlet of the stopcock, and approximately 3 ml of cerebrospinal fluid (CSF) is removed (CSF is not 'aspirated' since any negative pressure can be harmful, so the syringe plunger is drawn back before connecting the syringe, and the syringe with the drawn-back plunger is then connected to the 2nd outlet of the stopcock and the CSF thus flows into the syringe).
6. The syringe containing the CSF is removed and closed, the air is removed from the syringe and the syringe is then again placed at the 2nd outlet of the stopcock. The CSF is injected back only after the injection of the MSC-NTF as described below.
7. A second syringe containing a 4 ml suspension of MSC-NTF cells is attached to the 3rd outlet of the valve, and the cells are injected over roughly 2 minutes.
8. The stopcock is then immediately turned back to the 2nd outlet and approximately 1 ml of the previously collected CSF is injected, "washing" the spinal needle and ensuring that the entire cell suspension is transplanted into the patient.

9. The procedure is completed by withdrawing the needle and immediately placing pressure on the puncture site.
10. The syringe containing the remaining 2 mL of CSF is removed and capped and should be transferred to storage at -80°C within 30 minutes of the completion of the procedure.
11. The patient is typically asked to lie on his/her back for at least 2 hours, on an anti-Trendelenburg position and is monitored for signs of neurological problems.

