6.2.3. Exploratory Objectives

To compare the slopes of decline of hand-held dynamometry (HHD), and electrical impedance myography (EIM, for patients in whom this optional outcome measure is available) against placebo as well as during the 12-16 week pre-transplant monitoring period relative to the 24 week post-transplant follow-up period.

Determine feasibility of succeeding in blinding patients and caregivers to the treatment, in anticipation of a requirement to include the placebo group in the Phase III efficacy study.

To examine the CSF of ALS patients at baseline and two weeks after treatment for the presence of neurotrophic factors and possible ALS biomarkers.

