6.5.3.5. Visit 5: Cell Transplantation (Days 0-2) 24-38 days from BMA

At the transplantation visit, subjects will be admitted to an inpatient study unit for study procedures. Pre-transplant activities will include:

- Review of concomitant medications
- Review of adverse events
- Vital sign measurements
- Directed physical examination including weight
- Neurological examination

- SVC pulmonary function test
- ALSFRS-R questionnaire
- Hand held dynamometry (HHD)
- Electrical impedance myography (EIM) will be collected only at centers that opt to participate in EIM data collection.
- Columbia Suicide Severity Rating Scale (C-SSRS) Since Last Visit

Following pre-transplant procedures, subjects will undergo intrathecal injection of cells or placebo as well as 24 intramuscular injections of cells or placebo (transplantation) along the biceps and triceps muscle of the right arm (If the physician is unable to inject into the right arm, the cells may be injected into the left arm and the fact recorded on the CRF. See Appendix 4, describing the procedure for the IM injections). CSF removed from the subject immediately prior to the intrathecal administration of cells will be retained for analysis.

Concomitant medications and adverse events will be monitored throughout the study visit, as necessary. In addition the following will be monitored:

- Vital signs will be monitored at hours 1, 2, 3, 4, 6, 16, 22, 28, 40, and upon discharge at 44 hours or up to 72 hours post transplantation. Inpatient observation is up to 72 hours, with earlier discharge at investigator discretion.
- Visual inspection of the injection sites will be performed at hours 1, 16 and 40.
- Directed physical examinations will be performed at hours 16, and 40 post-transplantation.
- Hematology, coagulation chemistry evaluations and biochemistries as well as urinalysis will be checked at 16 hours.
- Electrocardiogram (ECG) will be performed at 22 ± 4 hours post-transplantation

Prior to discharge, activities will include: vital signs, review of medications and adverse events and questionnaire for assessment of blinding.

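### The baseline CSF sample is not isolated before dosing: it is what is left in the wash syringe, so product carry-over cannot be excluded (exploratory CSF endpoint only)

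*Protocol*

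**What the plan says.** The exploratory objectives (Protocol 6.2.3) include: "To examine the CSF of ALS patients at baseline and two weeks after treatment for the presence of neurotrophic factors and possible ALS biomarkers". Section 6.9.3.3 says that the assays, still to be developed, target neurotrophic factors because the cells secrete them. For the baseline sample, Visit 5 (6.5.3.5) states: "CSF removed from the subject immediately prior to the intrathecal administration of cells will be retained for analysis". The visit lists show no earlier CSF collection. The Week 2 sample is 3 mL from a separate lumbar puncture (6.5.4.1).

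Appendix 3, section 6.15.3.2, sets the order of handling:

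- Step 5: "approximately 3 ml of cerebrospinal fluid (CSF) is removed", into one syringe on the 2nd outlet.
- Step 6: the syringe is taken off, closed and cleared of air, and "the syringe is then again placed at the 2nd outlet of the stopcock".
- Step 7: "A second syringe containing a 4 ml suspension of MSC-NTF cells is attached to the 3rd outlet of the valve"; injection follows.
- Step 8: "The stopcock is then immediately turned back to the 2nd outlet and approximately 1 ml of the previously collected CSF is injected", to wash the needle.
- Step 9: the needle is withdrawn.
- Step 10: "The syringe containing the remaining 2 mL of CSF is removed and capped and should be transferred to storage" at -80°C.

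The placebo is DMEM (6.3.3.2).

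**The concern.** Visit 5 describes the retained fluid as CSF taken before dosing. That is true of when it was drawn, but not of how it was kept. The syringe stays on the stopcock while the product goes through, is opened to the product path for the wash, and is capped only at the end. No step sets aside an aliquot beforehand, closes the 2nd outlet after the wash, or checks for or removes cells before freezing.

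The analytes are substances that the product secretes, so carry-over would act on exactly what is being measured, and differently by arm: cells and their factors in the active arm, cell-free medium in the placebo arm. The Week 2 sample has no product in its collection path, so the two time points are not collected alike. A baseline that is too high in treated patients would hide part of a real rise, and it cannot be collected again after dosing.

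**Working it through.** **1. Which fluid is stored.** Step 5 draws about 3 mL, step 8 returns about 1 mL, and 3 − 1 = 2 mL. This matches the 2 mL in step 10, so the stored sample is the wash remainder and not a separate aliquot.

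**2. Can product reach it?** The syringe is reattached at step 6, before the cells, and is re-opened to the product path at step 8. Flow at step 8 is out of the syringe, so contamination needs backflow or mixing. Two features make backflow possible. Step 5 relies on CSF flowing unaided into a syringe on this same outlet. By the end of step 8 the net volume added is 4 + 1 − 3 = 2 mL, and no step closes the outlet before the needle is withdrawn.

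**3. Concentration of the product.** The synopsis gives 100–125 × 10⁶ cells in 4 mL (4,000 µL):

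- 100 × 10⁶ / 4,000 = 25,000 cells per µL
- 125 × 10⁶ / 4,000 = 31,250 cells per µL

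**4. Effect on the assay.** Two inputs are not in the documents and are assumed here for illustration only:

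- v, the volume carried back: 0 to 100 µL.
- k, the assayable factor per unit volume of suspension relative to the patient's own CSF: 10 to 1,000 for cells. For DMEM k = 0.

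Measured baseline / true baseline = (2,000 + v·k) / (2,000 + v).

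| v (µL) | cells carried over, active arm | k = 10 | k = 100 | k = 1,000 | placebo (k = 0) |
|---|---|---|---|---|---|
| 0 | 0 | 1.00 | 1.00 | 1.00 | 1.00 |
| 1 | 25,000–31,250 | 1.004 | 1.049 | 1.499 | 0.9995 |
| 10 | 250,000–312,500 | 1.045 | 1.493 | 5.970 | 0.995 |
| 100 | 2.5–3.1 million | 1.429 | 5.714 | 48.571 | 0.952 |

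Example, 10 µL at k = 100: (2,000 + 1,000) / 2,010 = 1.493.

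**5. Effect on the change to Week 2.** The Week 2 value is unaffected, so the measured fold change is the true fold change divided by the ratio above. At 1.045 it is 1/1.045 = 96% of the true value; at 1.493 it is 1/1.493 = 67%. If k were 1 or less, the baseline would not be inflated at all.

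**6. If the sample is isolated first.** Then v = 0 and the ratio is 1.00 in both arms.

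**The case against.** The strongest case against is that the mechanism is only a possibility. Turning the stopcock back at step 8 implies that the CSF outlet was out of the fluid path while the cells went in. The wash then pushes CSF outward, so afterwards the path should hold mainly CSF. All of this stands.

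It also stands that the size rests on two undocumented inputs. Cell counts are not assay signal, and on the assumed values the ratio runs from 1.00 to almost 49. The table shows what the result depends on; it does not estimate the effect.

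A reader might infer that active-arm baselines are contaminated and that the randomised comparison of CSF change is therefore biased. The documents support neither step. They do not show that carry-over occurs, and the visible text specifies no between-arm test of CSF change. Exploratory text in the SAP is redacted, so the planned contrast and any sample rule cannot be checked. A comparison of the arms at Week 2 alone would not be touched.

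Nor is the syringe first reconnected after the cells have passed: step 6 comes before step 7.

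What the objection does not answer is that the sample used as a pre-dose baseline is not secured before the dose, and nothing later in the procedure would reveal a problem.

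**Conclusion.** The point holds as a low-cost improvement to an exploratory measure. Appendix 3 leaves the only baseline CSF sample open to product carry-over that would differ by arm, and any resulting inflation would understate the active-arm rise to Week 2. Whether it happens, and how much, is unknown: anything from no effect to a material one is compatible with the documents. This rests on reading Appendix 3 as complete, with no separate aliquot or cell-removal step in a manual not available here. The primary safety assessment and the ALSFRS-R and SVC analyses are not affected, and no sample size, power or alpha changes.

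**What to change.** At step 6 the CSF syringe is already off the stopcock and closed. Add there, for both arms: transfer about 2 mL aseptically to a capped sterile storage container before the product syringe is connected, and put back only the remaining 1 mL or so for the wash. Amend step 10 so that the storage instruction and its 30-minute limit refer to that container. The dose, the volumes withdrawn and returned, and the injection sequence stay as they are.

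Add a CRF field for the handling used. In the CSF analysis, flag samples stored under the present procedure and interpret their change from baseline with that caveat. SAP 6.3 reports a completed blinded data review, so for samples already collected the flag may be all that remains possible.

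The cost is one sterile container per patient, a brief aseptic transfer, one CRF field and a short edit to Appendix 3.

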6.15.4. Appendix 4: Procedure for IM transplantation of MSC-NTF cells

The purpose of this document is to describe the procedure and define the basic requirements for Intramuscular (IM) transplantation of BrainStorm's proprietary MSC-NTF cells in clinical trials.

The procedure described here is based on common clinical practice (IM injection) as well as the experience of the medical staff currently conducting the company's clinical trial at the Neurology Department of the Hadassah Medical Center in Jerusalem.

6.15.4.1. Product Handling and injection procedures

All syringes should be gently rotated for 20-30 seconds until all cells are in suspension.

For IM injections remove syringe cap and connect a 25Gx5/8" (0.5x16mm) needle.

[figure not shown]
With the needle in the upright position gently flick the syringe to surface any trapped bubbles. Push the plunger up until the first drop is visible at the tip of the needle. At this point the product is ready for injection.

6.15.4.2. Procedure:

1. For IM transplantation of MSC-NTF cells, the patient may be in a reclining or upright position. The upper arm area is prepped using aseptic technique. In case of a hairy arm the arm is shaved prior to IM injections.
2. The syringes for IM injection contain an 0.32 ml suspension of MSC-NTF cells, in a 1 ml Luer-Lock syringe (such as: Becton Dickinson Cat. No. 309628), attached to a 25Gx5/8" (0.5 x 16 mm, such as Becton Dickinson Cat. No. 300600) needle.
3. The MSC-NTF cell suspension (0.2 ml) is transplanted into the patient by multiple intramuscular injections (IM) to a 1.5 cm depth (ensuring that injection is into the muscle and not into adipose tissue) at 24 separate sites on the patient's right upper arm biceps and triceps muscles, according to a map based on the designed grid (see below).
4. The procedure is completed by withdrawing the needle.
5. The patient's arm is bandaged with a pressure bandage
6. The patient is typically asked to remain in the clinic area for at least 2 hours, and is monitored for signs of neurological problems.

6.15.4.3. GRID FOR BICEPS & TRICEPS MUSCLES IM INJECTION

6.15.4.3.1. Grid of Triceps

6.15.4.3.2. Grid of Biceps

DSMB	Data and Safety Monitoring Board
ECG	Electrocardiogram
eCRF	Electronic Case Report Form
EDC	Electronic Data Capture
EIM	Electrical Impedance Myography
FAS	Full Analysis Set
G-CSF	Granulocyte Colony Stimulating Factor
GDNF	Glial Derived Neurotrophic Factor
Gluc	Glucose
HCO3	Bicarbonate
Hct	Hematocrit
HDL	High Density Lipoprotein
Hgb	Hemoglobin
HGF	Hepatocyte Growth Factor
██████████	██████████
HR	Heart Rate

Abbreviation	Definition
ICH	International Conference on Harmonization
IM	Intramuscular
INR	International Normalized Ratio
IT	Intrathecal
K	Potassium
LDL	Low Density Lipoprotein
LIF	Leukemia Inhibitory Factor
MCH	Mean Corpuscular Hemoglobin
MCHC	Mean Corpuscular Hemoglobin Concentration
MCMC	Monte Carlo Markov Chain
MCV	Mean Corpuscular Volume
MedDRA	Medical Dictionary for Regulatory Activities
Mg	Magnesium
mFAS	Modified Full Analysis Set
mmHg	Millimeters of Mercury
msec	Milliseconds
MSC-NTF	Mesenchymal Stem Cells Secreting Neurotrophic Factors
Na	Sodium
Phos	Phosphate
PP	Per-Protocol
PT	Preferred Term or Prothrombin Time depending on usage
PTT	Partial Thromboplastin Time
RBC	Red Blood Cell
SAE	Serious Adverse Event
SAP	Statistical Analysis Plan
SD	Standard Deviation
SDC	Statistics & Data Corporation
SE	Standard Error
SI	Standard International
SOC	System Organ Class
SOP	Standard Operating Procedure
SVC	Slow Vital Capacity
TG	Triglyceride
VEGF	Vascular Endothelial Growth Factor

Abbreviation	Definition
WBC	White Blood Cell
WHO-DD	World Health Organization Drug Dictionary

1. Introduction

This statistical analysis plan (SAP) describes the planned analysis and reporting for protocol BCT-001-US, entitled “A phase 2, randomized, double blind, placebo-controlled multicenter study to evaluate safety and efficacy of transplantation of autologous mesenchymal stem cells secreting neurotrophic factors in patients with Amyotrophic Lateral Sclerosis”, Amendment 1, dated 23 Sept 2014. The purpose of this SAP is to describe the statistical methodologies that will be used to address the objectives of the above study and come to conclusions regarding the study objectives, ensuring their validity and suitability.

2. Study Objective

2.1 Primary Objective

The primary objective of this study is to evaluate the safety of transplantation of culture expanded autologous Bone Marrow derived MSC-NTF cells administered on a single occasion via combined intrathecal (IT) administration and 24 intramuscular (IM) injections given into the right biceps and triceps muscles in patients with Amyotrophic Lateral Sclerosis (ALS).

2.2 Secondary Objectives

The secondary objectives of this study are

- To compare the change in slopes from the pre-transplantation period to the post-transplantation period in ALSFRS-R between the treatment and placebo groups through 12 and 24 weeks post-transplantation.
- To compare the change in slopes from the pre-transplantation period to the post-transplantation period in SVC between the treatment and placebo groups through 12 and 24 weeks post-transplantation.
- To compare the slope of the rate of decline in the ALSFRS-R at 12 and 24 weeks following transplantation relative to the 12-16 week Baseline period before transplantation in all patients (both treatment and placebo groups).
- To compare the slope of the rate of decline in SVC at 12 and 24 weeks following transplantation relative to the 12-16 week Baseline period before transplantation in all patients (both treatment and placebo groups).

[REDACTED]

[REDACTED]

- [REDACTED]
- [REDACTED]
- [REDACTED]
- [REDACTED]
- [REDACTED]
- [REDACTED]
- [REDACTED]

3. Study Design and Procedures

3.1 General Study Design

This is a Phase II, randomized placebo-controlled, multi-center, double blind study evaluating the safety and efficacy of combined intramuscular and intrathecal transplantation of MSC-NTF cells in participants with ALS. Forty-eight (48) participants will be treated from 3 medical centers in the United States.

3.2 Randomization

A blocked randomization scheme with a block size of 4 (ratio of 3:1 of active:placebo) that is stratified by site will be used. Site-specific randomization lists will be provided to the Production manager (unblinded personnel) prior to any subjects being randomized.

For each subject, at Visit 3, one week before bone marrow aspiration (BMA), the clinical site will notify the cell culture facility of the eligibility of a subject; the cell production facility personnel will then sequentially assign a randomization number according to the randomization list for each site.

3.3 Schedule of Evaluations

All participants will undergo informed consent and sign a written informed consent document. Participants will be informed that in case their autologous bone marrow fails to grow adequate numbers of MSC they will not receive the transplant. Any subject discontinuing the study prior to transplantation of cells (or placebo) injections were to be replaced with another participant to meet the target of 48 transplanted participants.

All participants will be observed for a total of 12-16 weeks pre-treatment and a 24 week post-treatment follow-up period.

All eligible participants will have a total of 50-70 ml of bone marrow aspirated about 9-11 weeks following the first Screening Visit. The participants will be randomized into either a treatment or a placebo group. MSC isolation and cell propagation will occur for participants in the treatment group; the process will last about 3-5 weeks and will be followed by MSC-NTF cell transplantation for subjects randomized to treatment.

and excipient (Dulbecco modified Eagle Medium, DMEM) transplantation for subjects randomized to placebo.

At the Transplantation Visit (about 12-16 weeks after the Screening Visit), subjects will be admitted to an inpatient study unit for study procedures and will be followed for 44 – 72 hours post-transplantation.

Following treatment, patients will be followed at least monthly for a total of 24 weeks by evaluators blinded to the treatment group, using identical procedures as during the pre-transplantation period. Participants will be followed by in-person visits and telephone visits at least monthly throughout the trial.

Each patient will thus be followed for a total of about 38 weeks (9 – 10 months) from the first Screening Visit. The clinical study flowchart is shown in Figure 1 below

[figure not shown]

Figure 1: Clinical Study Flowchart

The complete study schedule of activities including the assessments made at each visit and the detailed schedule of activities for cell transplantation at Visit 5 are shown in Table 1 and Table 2, respectively.

Table 1: Schedule of Activities

Study Period	Screening	Pre-transplantation period			Cells/Placebo Transplantation Visit	Post-transplantation follow-up							
		V2	V3	V4		V5	V6	V7	V8	Phone Call 1	V9	Phone Call 2	V10 EOS
Visit	Screening	Enrolment	BMA		Transplantation	Wk2	Wk 4	Wk 8	Wk 12	Wk 16	Wk 20	Wk 24	
Time Schedule			Precedes V2 by 4-6 wks	Wk 4-6	Wk 8-10	Wk 9-11	D0-2						
Informed consent	X												
Eligibility criteria	X	x											
Demographic data	X												
Height	X												
Body weight	X	x	x	x	X	x	x	x		x			x
Physical examination	X	x	x		X	x	x	x		x			x
12 lead ECG	X				X								x
Vital signs ¹	X	x	x	x	X	x	x	x		x			x
Medical History	X												
ALS Medical History	X												
El Escorial Criteria	X												
ALSFRS-R	X	x	x		X	x	x	x	x	x	x	x	x
Neurological Examination	X	x	x		X	x	x	x		x			x
EIM (Optional)	X	x	x		X	x	x	x		x			x
Slow Vital Capacity (SVC)	X	x	x		X	x	x	x		x			x
[REDACTED]	X	x	x		X	x	x	x		x			x
Concomitant medication review	X	x	x	x	X	x	x	x	x	x	x	x	x
HIV 1 and 2	X			x									

Study Period	Screening	Pre-transplantation period			Cells/Placebo Transplantation Visit	Post-transplantation follow-up						
		V2	V3	V4		V6	V7	V8	Phone Call 1	V9	Phone Call 2	V10 EOS
Visit	Screening	Enrolment	BMA	Transplantation								
Procedure												
Time Schedule	Precedes V2 by 4-6 Wks	Wk 4-6	Wk 8-10	Wk 9-11	D0-2	Wk 2	Wk 4	Wk 8	Wk 12	Wk 16	Wk 20	Wk 24
HBV	X		x									
HCV	X		x									
HTLV I and II	X		x									
Treponema pallidum	X		x									
CMV	X		x									
Pregnancy test	X		x									
Hematology ²	X		x		X		x	x		x		x
Blood biochemistry ³	X		x		X		x	x		x		x
Coagulation tests ⁴	X		x		X		x	x		x		x
Urinalysis ⁵	X		x		X		x	x		x		x
Bone marrow aspiration				x								
Cell Transplant IM / IT					X							
[REDACTED]					X	x						
Visual inspection of injection site					X							
Adverse events review		x	x	x	X	x	x	x	x	x	x	x
Prospective assessment of the occurrence of suicidality	X	x	x		X	x	x	x		x		x
[REDACTED]					X							x

1 HR, BP, Respiratory rate, Body temperature - Time Window: +/- 30 minutes

2 Hematology: CBC (RBC with Indices, WBC with differential and platelet count, Hb, Ht) - Time Window: +/- 2 hours

3 Blood Biochemistry: Na, K, Cl, HCO3, BUN, Cr, Glucose, Ca, Mg, Phosphorus, total protein, triglycerides (TG), Total cholesterol, HDL, LDL, urea, creatinine, total bilirubin, AST(GOT), ALT(GPT), ALP - Time Window: +/- 2 hours

4 Coagulation: PT, TT

5 Urinalysis (dip-stick test) - Specific Gravity, pH, glucose, protein, ketones, blood

Table 2: Detailed Schedule of Activities for Cell Transplantation Visit (V5)

1 Time Window: +/- 1 hour

2 HR, BP, Respiratory rate, Body temperature - Time Window: +/- 30 minutes

3 Ongoing data collection throughout visit as necessary

4 Hematology: CBC (RBC with Indices, WBC with differential and platelet count, Hb, Ht) - Time Window: +/- 2 hours

5 Blood Biochemistry: Na, K, Cl, HCO₃, BUN, Cr, Glucose, Ca, Mg, Phosphorus, total protein, triglycerides (TG), Total cholesterol, HDL, LDL, urea, creatinine, total bilirubin, AST(GOT), ALT(GPT), ALP - Time Window: +/- 2 hours

6 Urinalysis (dip-stick test) - Specific Gravity, pH, glucose, protein, ketones, blood

7 Coagulation PT, PTT

8 Can be done prior to discharge

4. Study Treatment

The investigational products for this study will be

- MSC-NTF cells
- Placebo (Dulbecco Modified Eagle Medium, DMEM)

IT Transplant Procedure: Participants will undergo a lumbar puncture (Spinal needle 20GA 3.50 IN (0.9 x 90 mm)) followed by intrathecal injection of cells or placebo (DMEM).

IM Transplant Procedure: Participants will undergo a unilateral (right) IM transplantation of cells or placebo solution (DMEM) into 24 sites in the upper arm.

The study flowchart described above is shown in Figure 2.

[figure not shown]

Figure 2: Study Groups Flowchart

5. Sample Size

This is a Phase II study for which no formal sample size calculation has been performed. The sample size chosen was not based on statistical considerations. The total of 36 treatment and 12 placebo subjects are expected to be a sufficient number to obtain adequate characterization of common treatment emergent adverse events and to observe trends for treatment effects on the efficacy measures chosen for this study. Additionally, with 36 subjects in the MSC-NTF treatment group, the study has 95% probability of seeing adverse events that occur at a true rate of 8% or greater. Therefore, if an adverse event of a specific type does not occur, there is 95% probability that the true rate of the adverse event is less than 8%.

6. Analysis Populations

